1.2.6 Safety profile of rituximab

No dose-limiting effects were observed in the Phase I/II studies. Reported adverse events including fever, chills, headache, nausea, vomiting, rhinitis, asthenia, and hypotension, occurred primarily during rituximab infusions and typically responded to an interruption of the infusion and resumption at a slower rate.

- **Fatal Infusion Reactions:** Severe and fatal cardiopulmonary events, including angioedema, hypoxia, pulmonary infiltrates, acute respiratory distress syndrome, myocardial infarction, and cardiogenic shock, have been reported. These severe reactions typically occurred during the first infusion with time to onset of 30-120 minutes.
- **Cardiac Events:** Patients with preexisting cardiac conditions, including arrhythmia and angina, have had recurrences of these cardiac events during rituximab infusions.
- **Tumor Lysis Syndrome:** Tumor lysis syndrome has been reported and is characterized in patients with a high number of circulating malignant cells ($\geq 25,000$ μ l) by rapid reduction in tumor volume, renal insufficiency, hyperkalemia, hypocalcemia, hyperuricemia, and hyperphosphatemia.
- **Renal Events:** Rituximab has been associated with severe renal toxicity including acute renal failure requiring dialysis, and in some cases has led to death. Renal toxicity has occurred in patients with high numbers of circulating malignant cells ($\geq 25,000/\text{mm}^3$) or high tumor burden who experience tumor lysis syndrome and in patients administered concomitant cisplatin.
- **Mucocutaneous Reactions:** Severe bullous skin reactions, including fatal cases of toxic epidermal necrolysis and paraneoplastic pemphigus, have been reported in patients treated with rituximab. The onset of reaction has varied from 1 to 13 weeks following rituximab exposure.

- **Hematologic Events:** In clinical trials, Grade 3 and 4 cytopenias were reported in 48% of patients treated with rituximab; these include: lymphopenia (40%), neutropenia (6%), leukopenia (4%), anemia (3%), and thrombocytopenia (2%). The median duration of lymphopenia was 14 days (range, 1 to 588 days) and of neutropenia was 13 days (range, 2 to 116 days). A single occurrence of transient aplastic anemia (pure red cell aplasia) and two occurrences of hemolytic anemia following Rituximab therapy were reported. In addition, there have been a limited number of postmarketing reports of prolonged pancytopenia, marrow hypoplasia, and late onset neutropenia.

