1.3.2 Endpoints to test simultaneous vs. delayed rituximab

The primary endpoint is whether simultaneous cladribine and rituximab cause a lower rate of MRD at 6 months than cladribine alone. Based on studies of rituximab for MRD after CdA [41, 47], CR

without MRD should be achieved in > 90% at 6 months after cladribine + rituximab. CR without MRD should be about 40-60% after cladribine alone, depending on whether or not patients had prior cladribine [11, 39, 40, 42-46]. However, a significant difference at 6 months would not indicate superiority in the clinical outcome of simultaneous cladribine + rituximab over cladribine alone, since delayed rituximab after 6 months might work better if it had not been used previously. Therefore, the major secondary endpoint will be to assess blood MRD-free survival not only after cladribine, but also after up to 2 rituximab courses given if needed for MRD in blood. BMBx IHC, blood and bone marrow aspirate FACS will be used for detecting MRD for the primary endpoint. However, since non-compliance with BMBx is expected to increase with longer follow-up, MRD-relapse for the secondary endpoints for need for delayed rituximab will need to be determined by blood tests, either blood FACS positivity or presence of cytopenias (ANC < 1500/ul, Plt < 100,000/ul, or Hgb < 11 g/dl). Patients FACS-negative in both blood and bone marrow aspirate are considered in MRD-negative CR regardless of blood counts. FACS, consensus PCR and IHC are all CLIA certified tests. Patients with 'dry' bone marrow or bone marrow unable to be aspirated will be considered MRD+, since in MRD-free CR, the bone marrow aspirate should be liquid and able to be aspirated. RQ-PCR, which is the most sensitive test, will also be observed, but will not be used for clinical decisions or statistics because it is early in its development, particularly in following HCL after chemotherapy. If patients achieve significantly longer time MRD-free survival after cladribine + rituximab than after cladribine alone, but shorter MRD-free survival after delayed rituximab if rituximab was used previously with cladribine, this will argue against changing the standard treatment for HCL from cladribine alone. The delayed rituximab in the trial design also permits several secondary scientific objectives (see Section 1.1.2) to be investigated for rituximab alone, including 1) determining if MRD levels and tumor markers (soluble CD25 and CD22) after rituximab correlate with response and tumor burden, 2) determining if BMBx can be avoided for judging response in HCL after rituximab, and 3) determining the effect of rituximab on normal B-cells without interference from simultaneous or recent cladribine.

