
1.3.3 Inability to assume that rituximab should be used with cladribine

Before a trial begins it is optimal for neither arm of a randomized trial to be obviously more advantageous than the other. There are potential advantages and disadvantages of simultaneous vs. delayed rituximab. It is possible, for example, that rituximab could have been more effective when begun at least 6 months after cladribine than concurrently, because by that time masses of tumor cells in the marrow, spleen and lymph nodes, which would present a tumor penetration problem for the rituximab Mab, might be at their minimum size. Secondly, if simultaneous rituximab were to fail to eliminate MRD, it could select for cells deficient in apoptosis and render patients unresponsive to rituximab and other agents when relapse occurs later in the disease course. Moreover, it is possible that the risk of infection could increase with combined use of rituximab and cladribine, since rituximab is known to cause rapid and prolonged (3-6 month) depletion of normal B-cells [57]. While this may not be a significant problem after single-agent short-course rituximab, it may be more problematic with the longer 8-cycle course, particularly after cladribine. Thus, a randomized trial was needed to determine if rituximab should be used with cladribine or delayed until after MRD appears. At this time, it is not considered standard to combine rituximab with cladribine for first-line or second-line treatment of HCL.

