3.3.3 DLT criteria

Grade III-IV cladribine or rituximab related toxicity except:

- Grade 3-4 hematologic toxicity resolving in 2 weeks is not DLT.
- Grade 3 fever is not DLT.
- Grade 3 gastrointestinal toxicity for < 5 days is not considered DLT.
- Severe or life-threatening anaphylaxis or hypersensitivity reaction

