4 SUPPORTIVE CARE

4.1 INFECTIONS/FEVER AND NEUTROPENIA

Febrile neutropenia is a common side-effect of cladribine which require empiric antibiotics, either as an inpatient or outpatient. Hematopoietic growth factors may be used if clinically indicated. Fever is also common with rituximab and may be treated symptomatically and with interrupting or with decreasing the infusion rate, as detailed in Section 13.2.6. Patients may receive prophylactic valacyclovir and less commonly prophylactic Bactrim if judged by the PI to be at significant risk of Herpes Zoster and Pneumocystis infections, respectively. Generally, prophylaxis will extend from the beginning of cladribine treatment until at least the 3-month time point when reassessments of CD4 and other blood counts are possible. If they have an allergy to Bactrim, Pentamidine or other medications/treatments may be ordered instead. Pneumocystis is extremely rare in HCL, particularly in newly diagnosed patients, allowing its prophylaxis to be reserved for patients with high risk, for example with very low CD4 counts or a prior history of infection.

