13.2.2 Toxicities (% grade 3, grade 4) in non-Hodgkin's lymphoma

13.2.2.1 Body as a Whole: fever (53, 1%), chills (33, 3%), infection (31, 4%), asthenia (26, 1%), headache (19, 1%), abdominal Pain (14, 1%), pain (12, 1%), back Pain (10, 1%), throat Irritation (9, 0%), flushing (5, 0%)

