13.2.2.11 Hematologic Events: In clinical trials, Grade 3 and 4 cytopenias [79] were reported in 48% of patients treated with RITUXAN; these include: lymphopenia (40%), neutropenia (6%), leukopenia (4%), anemia (3%), and thrombocytopenia (2%). The median duration of lymphopenia was 14 days (range, 1 to 588 days) and of neutropenia was 13 days (range, 2 to 116 days). A single occurrence of transient aplastic anemia (pure red cell aplasia) and two occurrences of hemolytic anemia following RITUXAN therapy were reported. In addition, there have been a limited number of post-marketing reports of prolonged pancytopenia, marrow hypoplasia, and late onset neutropenia (defined as occurring 40 days after the last dose of RITUXAN) in patients with hematologic malignancies. In reported cases of late onset neutropenia (NCI-CTC Grade 3 and 4), the median duration of neutropenia was 10 days (range 3 to 148 days). Documented resolution of the neutropenia was described in approximately one-half of the reported cases; of those with documented recovery, approximately half received growth factor support. In the remaining cases, information on resolution was not provided. More than half of the reported cases of delayed onset neutropenia occurred in patients who had undergone a prior autologous bone marrow transplantation. In an adequately designed, controlled, clinical trial, the reported incidence of NCI-CTC Grade 3 and 4 neutropenia was higher in patients receiving RITUXAN in combination with fludarabine as compared to those receiving fludarabine alone (76% {39/51} vs. 39% {21/53}) [80].

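### The DLT rule in section 3.3.3 does not exempt lymphopenia, so read literally an expected drug effect ends treatment and bars delayed rituximab

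*Combined protocol and SAP*

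**What the plan says.** Section 3.3.3 defines DLT as any grade III-IV toxicity related to either drug, followed by a list of exceptions. The haematologic entry is: "Grade 3-4 hematologic toxicity resolving in 2 weeks is not DLT". Nothing in that section, or elsewhere in the protocol, treats lymphopenia separately.

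Section 3.3.1 states the consequence: a patient with a DLT is off treatment, may be followed, and may not be retreated. Section 3.8.1 lists DLT, without qualification, among the criteria for removal from protocol therapy.

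The protocol describes the effect on lymphocytes in several places.

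- Section 1.2.6: "Grade 3 and 4 cytopenias were reported in 48% of patients treated with rituximab". Both 1.2.6 and 13.2.2.11 put grade 3-4 lymphopenia at 40% and give a median lymphopenia duration of 14 days, with a range of 1 to 588 days. The heading of 13.2.2 shows that these are toxicities "in non-Hodgkin's lymphoma".
- Section 1.3.3: "rituximab is known to cause rapid and prolonged (3-6 month) depletion of normal B-cells".
- Section 4.1 handles the infection risk by prophylaxis, generally from the start of cladribine "until at least the 3-month time point when reassessments of CD4 and other blood counts are possible".

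Section 3.2.2 plans delayed rituximab for all patients in whom HCL is found by blood FACS at least 6 months later. Section 1.3.2 makes blood MRD-free survival the major secondary endpoint, assessed not only after cladribine "but also after up to 2 rituximab courses given if needed for MRD in blood".

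**The concern.** The stopping rule and the rest of the protocol treat lymphocyte depletion in opposite ways. Elsewhere it is expected, covered by prophylaxis, and studied as a secondary objective in its own right (1.1.2, effects on normal T- and B-cells). Under 3.3.3, grade 3-4 lymphopenia that has not resolved at two weeks is a reason to stop.

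A patient with prolonged lymphopenia and no infection would lose any remaining doses of the current 8-dose course and could not receive delayed rituximab when MRD appears. The major secondary endpoint is meant to show how simultaneous and delayed rituximab compare once the later courses have been given. Withholding those courses for an expected laboratory effect would remove the treatment that the endpoint is meant to assess.

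**Working it through.** The plan states no figure for the frequency of this event, so there is nothing to reproduce. The check is mainly textual, with one illustrative calculation.

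**Step 1: scope of the rule.** Under the structure of 3.3.3, a related grade 3-4 toxicity that meets no exception is a DLT. The haematologic exception covers only toxicity that resolves within two weeks. It follows that related grade 3-4 haematologic toxicity lasting longer is a DLT. The section does not say this in a separate sentence, but it is the natural reading.

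**Step 2: is lymphopenia haematologic toxicity?** By the protocol's own classification, yes. Section 13.2.2.4 lists it under haematologic and lymphatic toxicities, and 1.2.6 and 13.2.2.11 list it under haematologic events.

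**Step 3: is it expected to last beyond two weeks?** The cited median of 14 days sits on the cut-off, and the upper end of the range is 588 days. Section 1.3.3 expects 3-6 months of normal B-cell depletion. That statement shows what the authors anticipated. It is not a toxicity grade and cannot be fed into the rule directly.

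**Step 4: what follows?** Sections 3.3.1 and 3.8.1 end treatment and exclude retreatment. DLT is not among the off-study criteria in 3.8.2, so the patient stays in follow-up without access to delayed rituximab.

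**Step 5: illustrative size.** Inputs:

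- share of rituximab-treated patients with grade 3-4 lymphopenia: 0.40 (1.2.6, 13.2.2.11);
- share of those episodes lasting more than 14 days: at most 0.50, because the median is 14 days. This assumes that the median, given for lymphopenia in general, applies to grade 3-4 episodes. The text does not say so.

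Share meeting the literal rule = share with grade 3-4 lymphopenia × share of episodes beyond 14 days.

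- With the share at its ceiling of 0.50: 0.40 × 0.50 = 0.20, so up to about 20%.
- With a share of 0.25: 0.40 × 0.25 = 0.10, or 10%.
- If the assumption about the median is dropped, the 20% ceiling no longer holds. A share of 0.75, for example, gives 0.40 × 0.75 = 0.30, or 30%.

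These figures come from rituximab in lymphoma, not from cladribine with rituximab in HCL. They apply only to patients given rituximab. They should not be applied to Arm 2 before delayed rituximab begins.

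**The case against.** The best defence is that no one would apply the rule this way, and several sections support it.

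- **Section 5.1** records an abnormal laboratory value as an adverse event only under stated conditions, such as symptoms, a need for treatment or clinical significance. Asymptomatic, expected lymphopenia might never be recorded, and so might never be called a related toxicity. This is arguable. However, 5.1 governs recording in the database, while 3.3.3 is written in terms of graded toxicity and does not refer to it.
- **Section 3.3.1** lets rituximab be delayed up to 12 weeks for toxicity, which shows that prolonged toxicity can be handled by waiting. The same section then bars retreatment after a DLT, and the delay allowance does not override that.
- **Section 5.1.1** defines the baseline for laboratory abnormalities. It does not exempt lymphopenia that is new or worse.
- **Relatedness** is required, but lymphopenia is a listed effect of rituximab, so this gives little protection.
- **The list in 3.3.3 is loosely drafted.** Severe anaphylaxis appears among its exceptions although 3.3.2 removes such patients. That suggests the intent differs from the text. It does not make the text right.

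The defence therefore makes the literal outcome less likely in practice but leaves the wording uncorrected.

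A reader might also infer that discontinuations will vary with the treating physician. The documents do not support this. Although some patients are treated outside NIH (5.1), the research team discusses each patient weekly and the principal investigator reviews every patient's adverse event and response data (10.4.1). Inconsistent application is possible but speculative.

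**Conclusion.** The point stands as a defect of wording. As written, 3.3.3 with 3.3.1 and 3.8.1 would stop treatment and bar delayed rituximab for prolonged grade 3-4 lymphopenia, an effect the protocol expects and manages by other means. This conclusion rests on the text and does not depend on the illustration.

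The size is uncertain. The figure of up to about 20% of rituximab-treated patients rests on lymphoma data and on the 14-day median holding for grade 3-4 episodes. Cladribine-related lymphopenia could raise it, but the documents give no figure. The 5.1 filter and investigator judgement could lower it.

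Three stronger readings are tempting and not supported:

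- That a fifth of this trial's patients have been or will be removed for lymphopenia. The documents contain no such data.
- That power or the 6-month primary comparison is damaged. No such effect can be derived from the documents.
- That the whole haematologic DLT definition needs narrowing. The problem is confined to lymphopenia. Requiring worsening from baseline would loosen the rule for severe neutropenia, thrombocytopenia and anaemia: 2.1.1.3 sets no lower limit on entry ANC or platelets, so a patient already at the worst grade could never qualify. Restricting the rule to those three cytopenias would drop leukopenia and other haematologic toxicity.

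This is a cheap improvement, held with medium confidence.

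**What to change.** Add one bullet to section 3.3.3: *Isolated lymphopenia (including B- or T-cell depletion) of any grade or duration is not a DLT; related grade 3-4 infection remains one.* Leave the two-week rule for all other haematologic toxicity unchanged, with no new baseline clause and no list restricting it to particular cytopenias.

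The cost is a wording amendment to one section, with no added procedures and no change in sample size. The downside is a slightly looser stopping rule for prolonged isolated lymphopenia. The prophylaxis in 4.1 limits that risk, as does keeping related grade 3-4 infection as a DLT.

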3.4 PROTOCOL EVALUATION

3.4.1 Pre-treatment evaluation (See Section [2.4](#))

3.4.2 Evaluation during study (See Section [15.1](#))

3.4.3 Post Treatment Evaluation (Follow-up)

- Patient follow-up at least semiannually will continue by clinic visit, phone, or secure email using NIH approved system to determine disease-free and overall survival. In patients who develop progressive disease, follow up will continue by annual phone call only, to determine overall survival.
- Patients will be closely followed to determine resolution of grade IV toxicity.

3.5 CONCURRENT THERAPIES

- Patients may not receive other treatments for HCL while on study
- This research study protocol allows the subject to receive up to 16 infusions of rituximab. Even if the treatment is shown to be of benefit, additional infusions of rituximab beyond that allowed in the protocol cannot be given to the subject while she/he is participating in this study.

3.6 RADIATION THERAPY GUIDELINES

Radiation therapy for HCL is not permitted while on protocol. Subjects requiring radiation therapy will be considered off treatment but not off study.

3.7 COST AND COMPENSATION

3.7.1 Costs

NIH does not bill health insurance companies or participants for any research or related clinical care that participants receive at the NIH Clinical Center.

3.7.2 Compensation

Participants will not be compensated on this study.

3.7.3 Reimbursement

The NCI will cover the costs of some expenses associated with protocol participation. Some of these costs may be paid directly by the NIH and some may be reimbursed to the participant/guardian as appropriate. The amount and form of these payments are determined by the NCI Travel and Lodging Reimbursement Policy.

3.8 CRITERIA FOR REMOVAL FROM PROTOCOL THERAPY AND OFF STUDY CRITERIA

Prior to removal from study, effort must be made to have all subjects complete a safety visit approximately 30 days following the last dose of study therapy.

3.8.1 Criteria for removal from protocol therapy

- Voluntary patient withdrawal
- Non-compliance with treatment and tests (discretion of PI)
- The patient has received 16 infusions of rituximab
- Progressive disease after the 2nd course of rituximab
- Progression prior to finishing 2 courses of rituximab which is considered by the PI to be too rapid to treat with rituximab alone.
- Dose-limiting toxicity
- Intercurrent illness or medical circumstances making it unsafe to remain on treatment
- Radiation therapy
- Positive pregnancy test

3.8.2 Off-Study Criteria

- Voluntary patient withdrawal
- Non-compliance at discretion of PI
- Death
- Screen failure
- Off-Study Procedure is in Section **2.3**. The reason for removing patients from study will be documented in the CRF and the medical record.

- Patients in long-term CR may become temporarily ‘lost to follow-up’ but may intend to eventually follow-up with restaging and taking them off study prematurely might greatly compromise the long-term objectives of the study. Therefore, patients may be reported as ‘lost to follow-up’ and unavailable for follow-up testing, but may continue to be followed once contact resumes. Regular communication with patients will be done to minimize this occurrence.

4 SUPPORTIVE CARE

4.1 INFECTIONS/FEVER AND NEUTROPENIA

Febrile neutropenia is a common side-effect of cladribine which require empiric antibiotics, either as an inpatient or outpatient. Hematopoietic growth factors may be used if clinically indicated. Fever is also common with rituximab and may be treated symptomatically and with interrupting or with decreasing the infusion rate, as detailed in Section 13.2.6. Patients may receive prophylactic valacyclovir and less commonly prophylactic Bactrim if judged by the PI to be at significant risk of Herpes Zoster and Pneumocystis infections, respectively. Generally, prophylaxis will extend from the beginning of cladribine treatment until at least the 3-month time point when reassessments of CD4 and other blood counts are possible. If they have an allergy to Bactrim, Pentamidine or other medications/treatments may be ordered instead. Pneumocystis is extremely rare in HCL, particularly in newly diagnosed patients, allowing its prophylaxis to be reserved for patients with high risk, for example with very low CD4 counts or a prior history of infection.

4.2 BLOOD PRODUCT SUPPORT

Symptomatic anemia should be treated with appropriate red blood cell support. Transfusion is generally recommended if the hemoglobin falls below 8g/dL, but lower levels are acceptable particularly for younger patients. Recombinant erythropoietin may also be used. Platelets are generally given when the platelet count is < 10,000/mm³ or when there is bleeding.

4.3 CYTOKINE SUPPORT

Prophylactic filgrastim (G-CSF) or sargramostim (GM-CSF) is not indicated for cladribine in HCL but may be used in special situations, for example, when patients have serious neutropenic infections and it is considered desirable to resolve the neutropenia as soon as possible.

4.4 TUMOR LYSIS SYNDROME

Although tumor lysis syndrome, with fever, hyperkalemia, hyperuricemia, hypocalcemia, hyperphosphatemia, and decreased renal function have been reported in CLL with rituximab, this syndrome has not been reported in HCL with either rituximab or cladribine. Patients with high baseline uric acid may be treated prophylactically with allopurinol but this protocol will not mandate prophylaxis for this syndrome. Patients should be followed closely particularly during the first week of treatment when the chance of tumor lysis syndrome would be highest.

